5.2 Primary Endpoint

Difference in pain reduction between the control group and the experimental group since the baseline visit and the 6 month visit evaluated by Visual Analogue Scale (VAS).

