7.5.3. Treatment Visit (\pm 15 days)

At this clinic visit the subject will undergo the following evaluations:

- Treatment process.
- Study completion (if applicable).
- Adverse event monitoring.
- Deviation monitoring.
- Any change of medication will be collected.

7.5.4. 1 Month Visit (\pm 7 days)

At this clinic visit the subject will undergo the following evaluations:

- Any change of medication will be collected.
- Subjects will be asked to fill out standard questionnaires to assess (VAS, ODI, SF-12, DN4 and PGI-I).
- Subjects will be assessed for possible adverse events, if any.
- Adverse event monitoring.
- Deviation monitoring.

All applicable information will be documented on a CRF.

7.5.5. 2 Months Visit (\pm 14 days)

At this clinic visit the subject will undergo the following evaluations:

- Any change of medication will be collected.
- Subjects will be asked to fill out standard questionnaires to assess (VAS, ODI, SF-12, DN4 and PGI-I).
- Subjects will be assessed for possible adverse events, if any.
- Adverse event monitoring.
- Deviation monitoring.
- Subject questionnaire of treatment satisfaction.

All applicable information will be documented on a CRF.

7.5.6. 4 Months Visit (\pm 14 days)

At this clinic visit the subject will undergo the following evaluations:

- Any change of medication will be collected.
- Subjects will be asked to fill out standard questionnaires to assess (VAS, SF-12 and PGI-I).
- Subjects will be assessed for possible adverse events, if any.
- Adverse event monitoring.
- Deviation monitoring.

All applicable information will be documented on a CRF.

7.5.7. 6 Months Visit (\pm 20 days)

At this clinic visit the subject will undergo the following evaluations:

- Any change of medication will be collected.
- Subjects will be asked to fill out standard questionnaires to assess (VAS, ODI, SF-12, DN4 and PGI-I).
- Subjects will be assessed for possible adverse events, if any.
- Adverse event monitoring.
- Deviation monitoring.
- Subject questionnaire of treatment satisfaction.

All applicable information will be documented on a CRF.

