7.10 Definition of Population for Analyses

We define 3 different subject populations for analysis:

1. Intent-to-Treat (ITT)

- All subjects who receive any treatment of the groups (Experimental or Control)

2. Per Protocol (PP)

- All subjects who receive treatment of the study and complete the Primary Effectiveness Assessment (Primary Endpoint defined above).

3. ITT-Baseline (ITT-B)

- All subjects who complete baseline assessment. In order to capture AEs that occur prior to the 6 months follow-up visit.

8. – SAFETY ASPECTS

The definitions presented in this section allow for a clear understanding of adverse event data collection and reporting requirements.

Medical Device

Any instrument, apparatus, implement, machine, appliance, implant, software, material or other similar or related article.

Intended by the manufacturer to be used, alone or in combination, for human beings for one or more of the specific purpose (s) of:

- Diagnosis, prevention, monitoring, treatments or alleviation of disease,
- Diagnosis, monitoring, treatment, alleviation of, or compensation for, an injury,
- Investigation, replacement, modification, or support of the anatomy or of a physiological process,
- Supporting or sustaining life,
- Control of conception,
- Disinfection of medical devices and

Which does not achieve its primary intended action in or on the human body by pharmacological, immunological or metabolic means, but which may be assisted in its intended function by such means. The term 'medical device' is usually defined by national regulations.

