11.1 Insurance Policy

According with current clinical trial legislation, this clinical trial does not require an insurance policy since the devices under study are used under the authorized conditions of use and the study does not imply an increase in the risk to the patient.

12. - PUBLICATIONS RIGHTS

Principal Investigator shall have the right to publish the results of the Study in any abstract, paper, presentation or manuscripts (not limited enumeration).

Principal Investigator shall give BOSTON SCIENTIFIC a reasonable period of 30 (thirty days) to review and comment upon an intended publication of Principal Investigator regarding the results of the Study prior to publication, to determine if any Intellectual Property Rights and/or Confidential Information should be removed. BOSTON SCIENTIFIC shall respond promptly in writing to Principal Investigator with any comments or objections, setting forth such information in reasonably sufficient detail.

Principal Investigator shall consider BOSTON'S SCIENTIFIC comments and/or objections in good faith and shall cause any and all appropriate changes to be made prior to further distribution and publication.

13. - STATISTIC ANALYSIS

A descriptive analysis of the categorical variables was performed using absolute and determined frequencies; and in the numerical variables, through the mean and

standard or median deviation and 25th and 75th percentiles, according to compliance with the assumption of normality.

The analysis of the main variable, pain difference between baseline measurement and 6 months after treatment in the radiofrequency group plus steroids vs steroids, will be carried out using a contrast of means with the t-Student or U Mann-Whitney test in case of not being able to fulfill the corresponding assumptions.

The size of the effect is estimated with Cohen's letter, interpreting a Cohen's letter <0.01 as "very small", between 0.01 to 0.2 as a "small" effect, around 0.5 an "average" effect ", from 0.8 to infinity, a" large "effect, according to the categorization of Cohen and Sawilowsky (Cohen, Jacob (1988). Statistical analysis of power for behavioral sciences. Routledge; Sawilowsky, S (2009). "New effect size rules of thumb". Journal of Modern Applied Statistical Methods. 8 (2): 467–474.).

If the imbalance is observed between the two groups, linear regression will be executed to adjust for variables that are observed unbalanced between them.

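### The Section 7.10 analysis sets do not match their labels: ITT omits randomised patients who go untreated, PP has no adherence criterion, and both lead to the same primary test

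*Combined protocol and SAP*

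**What the plan says.** Section 7.10 defines three sets.

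- ITT: "All subjects who receive any treatment of the groups (Experimental or Control"). Treatment is required; a 6-month VAS is not.
- PP: "All subjects who receive treatment of the study and complete the Primary Effectiveness Assessment". The definition refers back to the primary endpoint and adds no other condition.
- ITT-B: "All subjects who complete baseline assessment. In order to capture AEs that occur prior to the 6 months follow-up visit".

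The primary endpoint in Section 5.2 is "Difference in pain reduction between the control group and the experimental group since the baseline visit and the 6 month visit". Section 13 names the primary variable as "pain difference between baseline measurement and 6 months after treatment in the radiofrequency group plus steroids vs steroids" and compares it "using a contrast of means with the t-Student or U Mann-Whitney test", with linear regression if the groups turn out unbalanced. Section 13 does not say which set is used for any analysis, and it gives no imputation, repeated-measures model or other method for missing values.

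Other sections bear on who falls in each set:

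- Section 7.2 leaves the allocation open to investigators.
- Section 7.5.2 places randomisation at the baseline visit, re-checks eligibility and records screening failures there, and allows (but does not require) treatment at the same visit.
- "Deviation monitoring" appears in Section 7.5.3 and at every later visit, and Table 1 agrees. It is not listed at screening or baseline.
- The 6-month visit has a window of ±20 days (Section 7.5.7).
- Section 5.3 lists procedure-related adverse events and unanticipated device effects as secondary endpoints, without naming a set.

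**The concern.** A reader expects ITT to mean everyone randomised, analysed as randomised, and PP to mean those who followed the protocol. Neither holds here.

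Restricting ITT to treated patients allows exclusion after randomisation by staff who know the arm. That can undo the comparability that randomisation provides.

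A PP set without adherence criteria cannot show what happens when patients with serious deviations are removed. Comparing ITT with PP is a common check on robustness. If both tests use the same patients, they agree by construction, and a report could mistake that for evidence.

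For safety, an event caused by the procedure can occur only in someone who had the procedure. The plan does not fix a treated denominator for those events.

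**Working it through.** **1. The plan's own sample size.** Inputs from Section 7.3: means 40 and 60 mm (difference 20 mm), SD 30 mm, two-sided 5% level, 90% power, 20% losses. The standardised difference is 20/30 = 0.667. A two-sample t-test calculation (noncentral t) gives 48.26, rounded up to 49 per group. Then 49/(1 − 0.20) = 61.25, rounded up to 62. The plan's figure is reproduced exactly. (The normal approximation gives 48, and 48/0.80 = 60.) So the 62 is built to leave about 49 patients per arm with a 6-month value.

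**2. Who enters each primary test.** A change score exists only if the 6-month VAS exists.

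- ITT test = (treated) and (has a 6-month VAS).
- PP test = (treated and completed the primary assessment) = (treated) and (has a 6-month VAS).

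The regression fallback needs the same outcome, so it uses the same patients. At the planned losses, 62 × 0.80 = 49.6 per arm. With 12 of 62 lost, both tests use the same 50, however the 12 divide between never treated and lost after treatment:

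| Never treated (assumed) | ITT on paper | PP | In the ITT test | In the PP test |
|---|---|---|---|---|
| 0 | 62 | 50 | 50 | 50 |
| 3 | 59 | 50 | 50 | 50 |
| 6 | 56 | 50 | 50 | 50 |
| 12 | 50 | 50 | 50 | 50 |

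No patient differs between the last two columns. Power is 90.4% at 49 per arm and 91.0% at 50; it would be 95.8% only if all 62 had data.

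**3. What PP removes.** The trial provides for four kinds of adherence information: eligibility (re-checked at baseline), procedure given, timing of the 6-month visit, and deviations (from the treatment visit onward). None appears in the PP definition. A treated patient who fails on any of them but has a 6-month VAS stays in.

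**4. Randomised but not treated.** Randomisation is at baseline and treatment may be a later visit, so a patient can be randomised and not treated. That patient is in ITT-B if the baseline assessment was completed, but not in ITT. The documents give no expected number.

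**5. Safety denominator.** If ITT-B were used for procedure-related events, the reported rate would be the true rate × (treated/62). The number untreated is an assumption, and the 10% true rate is illustrative:

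| Untreated of 62 | Factor | A true 10% reads as |
|---|---|---|
| 0 | 1.000 | 10.0% |
| 3 | 59/62 = 0.952 | 9.5% |
| 6 | 56/62 = 0.903 | 9.0% |
| 12 | 50/62 = 0.806 | 8.1% |

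One patient is 1/62 = 1.6 percentage points, so with up to 6 untreated the shortfall (at most 1.0 point) is smaller than one patient's event.

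**The case against.** The strongest reply is that the sets differ on paper by every treated patient lost before month 6, and coincide in the test only because Section 13 is silent on missing data. Any imputation or mixed model would separate them. That is correct, and it means the missing-data rule is part of the remedy: simply relabelling ITT as all randomised would, under the same t-test, again drop everyone without a 6-month VAS. As the plan now stands, however, the two tests are identical.

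Receiving study treatment, in the PP wording, might mean receiving all of it, as against any of it for ITT. The text does not say so, and even then eligibility, visit window and other deviations would be untouched.

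Several stronger readings are tempting, but the documents do not support them:

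- A reader might infer that ITT-B fails at its task. Its one stated task is to capture adverse events before the 6-month visit. Adverse events are assessed from the baseline visit onward, so it does capture them, including those before treatment.
- A reader might infer that procedure-related rates will be understated. No section makes ITT-B the denominator for those rates, and the treated set labelled ITT could serve. The gap is that no set is assigned.
- A reader might infer that screening failures are counted in ITT-B. Section 7.5.2 records them at baseline but does not say that they complete the baseline assessment.
- A reader might infer that the trial intends to present agreement between ITT and PP as robustness. Section 13 plans no such paired analysis; the risk lies in how the sets could be used.

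**Conclusion.** The point holds as a mismatch between labels and definitions. ITT is a treated set, not an all-randomised one. PP is a completer set with no adherence criterion. Under Section 13 as written, the primary test on either set uses the same 49 to 50 or so patients per arm, so the PP analysis adds no information. This rests on Section 13 naming no missing-data method and on the plan's 20% loss figure; the identity of the two samples does not depend on the size of the loss.

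The size of any bias from leaving out untreated randomised patients cannot be computed, because their number is not given.

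The safety part is narrower: procedure- and device-related events have no assigned treated denominator. If ITT-B were used, a true 10% rate would read between 10.0% and 8.1% over the assumed range of 0 to 12 untreated per arm. If baseline and treatment usually fall on the same visit, the dilution may be near zero.

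**What to change.** Rewrite Section 7.10 and link it to Section 13:

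1. **ITT.** Define it as all randomised patients, analysed in the arm to which they were randomised, and make it the main effectiveness set. State in Section 13 how a missing 6-month VAS is handled, so that the set does not collapse to completers.
2. **PP.** Define it as patients who met the entry criteria, received the assigned procedure, have a 6-month VAS within the ±20-day window and have no major deviation, from a list fixed before database lock. What counts as the assigned procedure must be settled first. Section 9.2 has the needle and electrode removed after experimental treatment with nothing given that could relieve pain, while the Summary, Section 7.3 and Section 13 describe that arm as radiofrequency plus steroids. These passages must be reconciled; until then the criterion cannot be applied to the experimental arm.
3. **Safety.** Rename the existing any-treatment set as the safety set, and use it, by procedure received, for procedure- and device-related events. Keep ITT-B for listing events from baseline onward, including those before treatment.

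The cost is mainly rewritten definitions, a missing-data rule, a deviation list and one extra safety table, with no new patients. The PP and safety sets use information already scheduled for collection. The all-randomised analysis is less certain on data: for early withdrawals Section 7.7 names only adverse events and medication use, so a 6-month VAS is not assured for those who withdraw. The missing-data rule has to cover them. All of this should be settled before database lock, because choosing exclusions once results are known would introduce bias.

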8.1 Adverse Events

The following adverse events will be recorded in the eCRF of the study:

- All serious adverse events.
- All adverse events considered of interest for this study, regardless of their seriousness.

NOTE - As the primary efficacy measure in this study is pain, leg and back pain does not need to be reported as an adverse event unless it meets the definition of a serious adverse event. However, Investigators may, at their discretion, report any pain-related adverse events during the study.

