5.3 Secondary Endpoints

- 5.3.1. Change from Baseline in pain at 1, 2 and 4 months (assessed by Visual Analogue Scale, VAS).
- 5.3.2. Change from Baseline in disability at 1, 2 and 6 months (assessed by Oswestry Disability Index, ODI).
- 5.3.3. Change from Baseline in health survey at 1, 2, 4 and 6 months (assessed by Short Form Health Survey, SF-12).
- 5.3.4. Change from Baseline in neuropathic pain at 1, 2 and 6 months (assessed by Douleur Neuropathique 4 Questions, DN4).
- 5.3.5. Assessment of improvement of pain with experimental procedure at 1, 2, 4 and 6 months (assessed by Patient Impression of Improvement, PGI-I).
- 5.3.6. Incidence of unanticipated adverse device effects.
- 5.3.7. Change in opioid intake in 6 months.
- 5.3.8. Adverse events related to procedures (experimental group and control group).
- 5.3.9. Assessment of subject satisfaction with experimental procedure at 2 and 6 months.

6. - ELIGIBILITY CRITERIA

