7.5.2. Baseline* (within 30 days from Screening Visit)

At this clinic visit the subject will undergo the following evaluations:

- Randomization.
- Eligibility criteria will be re-evaluated.
- Any change of medication will be collected.

- Subjects will be asked to fill out standard questionnaires to assess (VAS, ODI, SF-12 and DN4).
- Subjects will be assessed for possible adverse events, if any.
- AP and lateral view lumbar imaging.
- Screening failures will be collected.

*Baseline and Treatment visits could be at the same time.

All applicable information will be documented on a CRF.

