- 5-point scale where 1 is “very satisfied” to 5 that is “very dissatisfied”; their charging convenience and remote control use during the study visits: Months 2, 6 and if applicable at the Unscheduled visit. The responses will be summarized. Study personnel will be appropriately trained for administration of each test.

- Safety (device and procedures): Safety will be assessed by characterizing clinically meaningful change in adverse events at all study visits and in related to medical device or procedures.

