8.1.1 Serious Adverse Event (SAE)

An adverse event (AE) includes any unforeseen illness or injury or adverse clinical sign (including abnormal laboratory results) related or not to the investigational product. This includes events related to the product or to the comparator, or to the procedures involved.

It will be considered a serious adverse event (SAE) when:

- Causes death.
- It leads to a significant deterioration in the patient's health that results in:
 - Illness or injury that threatens life.
 - A permanent deterioration of a body structure or function.
 - Hospitalization or prolongation of hospitalization.
 - Medical or surgical intervention to prevent a life-threatening illness, injury or permanent disability of a body structure or function.
- Led to fetal distress, fetal death, or a congenital abnormality or birth defect.

Adverse events of interest for this study will be considered:

- Duration of the procedures greater than 1 hour.
- Problems related to the surgical wound.
- Infection.

NOTES:

- Planned hospitalization for a pre-existing condition, or a procedure required by the CIP, without serious deterioration in health, is not considered a serious adverse event.
- A pregnancy is not considered to be a serious adverse event but will be captured in the CRF as a non-serious adverse event to allow follow-up on the outcome of the pregnancy
- Examples for serious deterioration are: cardiac arrest (CPR required), CVA, paralysis, sepsis, amputation, internal/external bleeding, cancer, fracture requiring intervention, myocardial infarction.

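### The eCRF recording rule in section 8.1 is narrower than secondary endpoint 5.3.8, so non-serious procedure-related adverse events may be under-counted, and unevenly by site or arm

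*Combined protocol and SAP*

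**What the plan says.** Section 8.1 opens with a list of what goes into the eCRF: serious adverse events, and "All adverse events considered of interest for this study, regardless of their seriousness". Section 8.1.1 fills in the second class under the words "Adverse events of interest for this study will be considered", followed by three items: a procedure that runs past one hour, surgical wound problems, and infection. A note in 8.1.1 adds pregnancy as a non-serious event to be captured. A note in 8.1 exempts leg and back pain unless it is serious, on the ground that pain is the primary efficacy measure, and then says that "Investigators may, at their discretion, report any pain-related adverse events during the study".

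Other sections are not limited in this way:

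- Endpoint 5.3.8 is "Adverse events related to procedures (experimental group and control group"). No type or degree of seriousness is specified.
- Endpoint 5.3.6 is "Incidence of unanticipated adverse device effects".
- Section 7.6 states that "Safety will be assessed by characterizing clinically meaningful change in adverse events at all study visits", and goes on to those related to the device or procedures.
- At baseline, at months 1, 2, 4 and 6, and at unscheduled visits, section 7.5 has the line "Subjects will be assessed for possible adverse events, if any".
- Every visit section in 7.5 except the treatment visit (7.5.3) ends with "All applicable information will be documented on a CRF".
- Section 10.3 requires whatever information is collected to be entered in the CRF.

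**The concern.** Endpoint 5.3.8 can be no more complete than the eCRF entries behind it. If sites take 8.1 as the recording rule, an event that is non-serious, procedure-related and outside the three named types need not be entered, and may not be recoverable at analysis.

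Two features of the design make this more than a small loss of detail. There are six sites (Summary, item 7), which may read the rule differently. And section 7.2 leaves allocation open to the investigators. Pain reports made at discretion, and any other entry beyond the 8.1 list, could therefore depend on the arm. What is at stake is the comparison of procedural safety between radiofrequency plus steroid and steroid alone.

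**Working it through.** The plan gives no figure to reproduce, and no arithmetic decides the point. The check is to take types of event and ask what each rule does with them.

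| Event | Listed in 8.1 / 8.1.1? | Within 5.3.8? |
|---|---|---|
| Serious procedure-related event | Yes | Yes |
| Long procedure, wound problem or infection, non-serious | Yes | Yes, if procedure-related |
| Transient, non-serious leg motor deficit after the procedure | No | Yes |
| Non-serious leg or back pain flare after the procedure | Discretionary | Not excluded by 5.3.8 |

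**Third row.** Sections 9.1 and 9.2 both describe a check of leg motor function before discharge, so the plan itself creates the occasion to find such an event. A deficit amounting to paralysis would be serious under the 8.1.1 examples and would be recorded. A mild, short-lived one would not be on the list. The adverse event definition in 8.1.1 expressly takes in events related to the procedures.

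**Which rule governs?** Section 8 introduces its definitions as making adverse event collection and reporting clear, which favours 8.1 as the specific rule. Section 10.3 favours recording everything, but it applies to information that is collected, and a site could say that 8.1 defines what is collected. The visit sections cover only what is applicable. Section 7.5.3, the visit at which procedural events first arise, lacks even that sentence, although it does list adverse event monitoring. No text ranks these rules.

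**Other routes to the data.** Section 8.8 is vigilance reporting of serious or potentially serious device incidents; it is not eCRF capture. VAS scores carry no judgement of relatedness, so they cannot stand in for pain recorded as an adverse event.

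**Endpoint 5.3.6.** Section 8.3 defines the unanticipated class for serious device effects only. If 5.3.6 means that class, the 8.1 list supplies it. If it also covers non-serious device effects, it has the same gap as 5.3.8.

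**Feasibility.** Table 1 marks adverse event monitoring in 7 of its 8 visit columns (baseline, treatment, months 1, 2, 4 and 6, unscheduled), all but screening. The occasions to collect these events already exist.

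**The case against.** The strongest reply is that nothing conflicts. Section 8.1 does not say that only the listed events are recorded. Adverse events are assessed at visits, those found at early withdrawal go on a CRF (7.7), and 10.3 sends all collected information there. On that reading 8.1 merely names items that must never be missed. This stands in part: a reader might infer a flat contradiction, or a ban on recording other events, and the documents support neither. But a list of what will be recorded serves little purpose if everything is recorded anyway, and a site can reasonably follow it.

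A second reply is that targeted collection is a legitimate choice for CE-marked devices used within their indications, and that the three named events are largely procedural and so give effect to 5.3.8. That would be coherent, but 5.3.8 does not say so. It also means that the plan need not record every adverse event regardless of relation; 5.3.8 does not require that.

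Third, the pain exemption has a stated reason, and non-serious pain could be read as outside 5.3.8 unless reported. That reading is open, but it makes the content of an endpoint depend on the discretion of an unblinded investigator.

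Sections 7.8 and 8.7 might seem to add support. They add little. Section 7.8 concerns follow-up of device-related events, and the severity grading in 8.7 can be met by grading whatever is recorded. Section 7.6 is also qualified, since it speaks of clinically meaningful change.

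**Conclusion.** The point holds as a mismatch between a stated recording rule and a stated endpoint. A site applying 8.1 as written can omit non-serious procedure-related events that 5.3.8 counts, so 5.3.8 may be under-counted and may differ by site or arm.

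The limits are as follows. Serious adverse events and the primary VAS analysis are unaffected. Section 13 sets no safety hypothesis, so the effect is on the descriptive reading of 5.3.8 and on no stated test. The size cannot be derived: the documents give no complication rates and no information on how sites would read the rule, and any percentage would rest wholly on assumed values.

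A reader might infer that events will be lost, or that reporting will be biased between arms. The documents show only that the wording allows it. The adverse event page of the eCRF is not among the forms in Annex II; if it already captures all procedure- and device-related events, the defect is in the protocol wording alone. The wording should be corrected in either case.

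**What to change.** - Amend 8.1 so that the eCRF records, identically in both arms from the treatment visit to 6 months, all adverse events related or possibly related to the procedure or device, whatever their seriousness. This is in addition to everything 8.1 and 8.1.1 now list.
- Enter relatedness to procedure and relatedness to device as separate fields.
- Apply the same rule to new or worsened leg or back pain, in place of investigator discretion.
- Add to 7.5.3 the CRF documentation sentence that the other visit sections carry.
- State whether 5.3.6 covers non-serious device effects or only the class defined in 8.3.

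The cost is a change to protocol and eCRF wording, with modest extra data entry and checking. No visit is added. One weakness remains: relatedness is still judged by an investigator who knows the arm. Including possibly related events narrows the room for that judgement but does not remove it.
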